- Two recent case reports describe patients with pustular psoriasis unresponsive to TNF inhibition who responded to anti-IL-1 receptor therapy with anakinra.
- We hypothesize that monogenic and polygenic inflammatory pustular skin diseases share common pathogenic mechanisms mediated by IL-1.
- We propose a phase 2 study that will utilize a collaborative bench-to-bedside approach, applying targeted anti-IL-1 therapy, novel imaging modalities, and laboratory techniques including immunohistochemistry, gene expression and cytokine studies, and *in vitro* manipulations of skin to dissect and validate pathways in these complex diseases.

Objective:

- To characterize the clinical efficacy, optimal dosing and safety of anakinra in patients with pustular dermatoses.

Eligibility:

- Age \geq 18 years.
- Active macroscopic noninfectious pustular skin lesions involving \geq 5% of the total body surface area, or palmoplantar involvement.
- Histopathologic confirmation of epidermal neutrophilic pustulosis.
- Patients must have maintained a stable dose of immunosuppressant therapy, retinoids or anti-neutrophil therapy for 2 weeks prior to study initiation with resultant stable or worsening skin disease.

Abbreviated Title: Anakinra in pustular dermatoses

Version Date: December 12, 2018

- Use of biologic agents requires a washout period of at least 3 half-lives prior to study initiation.
- Patients must have organ and marrow function as defined below:
 - leukocytes $\geq 3,000/\text{mcL}$
 - absolute neutrophil count $\geq 1,500/\text{mcL}$
 - platelets $\geq 100,000/\text{mcL}$
 - creatinine within normal institutional limitsOR
 - creatinine clearance $\geq 60 \text{ mL}/\text{min}/1.73 \text{ m}^2$ for patients with creatinine levels above institutional normal.

Design:

- A 16-week, open-label phase 2 study.
- Patients will initially receive treatment with anakinra 100 mg/day by self-administered subcutaneous injection.
- Disease response will be assessed every 4 weeks, and determination of dose escalation will be made based on clinical assessment. Dose escalation can increase up to 200 mg/day, and for patients $>75 \text{ kg}$ up to 300 mg/day at the end of week 8.
- If a response is achieved with anakinra, other immunosuppressants administered for the purpose of treatment of pustular skin disease may be tapered per physician discretion.

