2 ELIGIBILITY ASSESSMENT AND ENROLLMENT

2.1 ELIGIBILITY CRITERIA

2.1.1 Inclusion Criteria

2.1.1.1 Females and males, aged ≥ 18 .

2.1.1.2 Patients must demonstrate active noninfectious inflammatory pustular skin lesions resembling pustular psoriasis and involving $\geq 5\%$ total body surface area, or palmoplantar involvement. Conditions may include, but are not be limited to, pustular psoriasis, Sneddon-Wilkinson disease, subcorneal pustular dermatosis, reactive arthritis, palmoplantar pustulosis, acrodermatitis continua of Hallopeau and palmoplantar pustular psoriasis.

2.1.1.3 Patients must have histopathologic confirmation of epidermal neutrophilic pustular skin disease.

2.1.1.4 If taking immunosuppressants, retinoids or anti-neutrophil therapy, participants must maintain stable doses of these medications during the 2 weeks prior to study initiation.

2.1.1.5 Patients must have stable topical medication regimen for 2 weeks prior to study initiation

2.1.1.6 Patients must have normal organ and marrow function as defined below:

- | | |
|-----------------------------|---|
| - leukocytes | $\geq 3,000/\text{mcL}$ |
| - absolute neutrophil count | $\geq 1,500/\text{mcL}$ |
| - platelets | $\geq 100,000/\text{mcL}$ |
| - creatinine | within normal institutional limits |
| | OR |
| - creatinine clearance | $\geq 60 \text{ mL/min/1.73 m}^2$ for patients with creatinine levels above institutional normal. |

2.1.1.7 Quantiferon TB Gold must be performed for screening for mycobacterium tuberculosis infection. However, a tuberculin skin test may be placed if the Quantiferon TB gold test is indeterminate (see below). Patients must have a negative Quantiferon TB Gold (or tuberculin skin test) or evidence of appropriate treatment prior to study entry (see below).

Negative Quantiferon TB gold	Begin study
Indeterminate Quantiferon TB gold	Place tuberculin skin test (TST). If negative, begin study.
Positive Quantiferon TB gold or TST	Negative CXR and ≥ 1 month Tx prior to 1 st dose of study drug

Abbreviated Title: Anakinra in pustular dermatoses

Version Date: December 12, 2018

- 2.1.1.8 Patients must be able to understand and sign a written informed consent document and complete study-related procedures and questionnaires.
- 2.1.2 Exclusion Criteria

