2.2 SCREENING EVALUATION

- Assessments to be completed prior to enrollment
 - Skin biopsy for hematoxylin and eosin staining to confirm diagnosis if prior confirmational biopsy has not been performed
 - Microbiologic culture of pustule confirming noninfectious etiology
- Assessments to be completed within 8 weeks prior to enrollment
 - Quantiferon TB gold
 - Chest X-ray to ensure absence of radiographic evidence of tuberculosis only if Quantiferon TB gold or tuberculin skin test is positive
 - Medical history and medication review
 - CBC with differential
 - Serum B-hCG in females of childbearing potential. Not required for females who are status-post hysterectomy or postmenopausal (no menses for >one year).
 - Blood urea nitrogen and serum creatinine
 - Anti-HIV-1/2 screen
 - Viral Markers Hepatitis Screen (HBsAg and anti-HCV)

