2.3 REGISTRATION PROCEDURES

2.3.1 Registration at the Clinical Center

Authorized staff must register an eligible candidate with NCI Central Registration Office (CRO) within 24 hours of signing consent. A registration Eligibility Checklist from the web site (<http://home.ccr.cancer.gov/intra/eligibility/welcome.htm>) must be completed and sent via encrypted email to: NCI Central Registration Office [contact]. After confirmation of eligibility at Central Registration Office, CRO staff will call pharmacy to advise them of the acceptance of the patient on the protocol prior to the release of any investigational agents. Verification of Registration will be forwarded electronically via e-mail to the research team. A recorder is available during non-working hours.

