2.3.2 For Participating Site Registration

A protocol registration form will be supplied by the NIAMS study coordinator and updates will be provided as needed. Subject eligibility and demographic information is required for registration. Once eligibility is confirmed, complete the protocol registration form which contains the eligibility checklist, indicating that the patient is being registered for treatment and send to NIAMS study coordinator. In addition, source documents supporting the eligibility criteria must be sent to the NIAMS study coordinator. The NIAMS study coordinator will notify you either by e-mail or fax that the protocol registration form has been received which will include the unique patient/subject ID number. Questions about eligibility should be directed to the study coordinator or PI. Questions related to registration should be directed to the study coordinator.

Abbreviated Title: Anakinra in pustular dermatoses

Version Date: December 12, 2018

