3.6 STUDY CALENDAR

	Screening ≤8 weeks prior to enrollment	Baseline- up to drug initiation ^a	Weeks 1, 2, 3 (+/- 3 days)	Week 4 (+/- 1 week)	Weeks 5, 6, 7 (+/- 3 days)	Week 8 (+/- 1 week)	Weeks 9, 10, 11 (+/- 3 days)	Week 12 (+/- 1 week): End of Treatm ent	Weeks 13, 14, 15 (+/- 3 days)	Week 16 (+/- 2 weeks): Post Therapy Follow- up ^a
Eligibility	X	X-update		Clinic visit		Clinic visit		Clinic visit		
Consent		X								
H&P	X	X- update		X		X		X		X
NIH Advanced Directives Form ^b		X								
Medication review	X	X- update		X		X		X		X
Dose titration ^c				X		X				
Telephone surveillance			X		X		X		X	
Immunosuppressant drug taper (per MD discretion)					X	X	X	X		
CBC/diff, serum creatinine and urea nitrogen, hepatic panel with alk. phos, serum B- hCG	X	X		X		X		X		X

Abbreviated Title: Anakinra in pustular dermatoses

Version Date: December 12, 2018

	Screening ≤8 weeks prior to enrollment	Baseline- up to drug initiation ^a	Weeks 1, 2, 3 (+/- 3 days)	Week 4 (+/- 1 week)	Weeks 5, 6, 7 (+/- 3 days)	Week 8 (+/- 1 week)	Weeks 9, 10, 11 (+/- 3 days)	Week 12 (+/- 1 week): End of Treatm ent	Weeks 13, 14, 15 (+/- 3 days)	Week 16 (+/- 2 weeks): Post Therapy Follow- up^a
Blood sampling: calcium, phosphorus, albumin, total protein, ESR, hs-CRP, serum c-peptide		X		X		X		X		X
Urine sampling: UA, calcium, phosphorus		X		X		X		X		X
Ferritin, lipid panel, serum insulin, serum glucose		X								
Serum and urine protein electrophoresis, Parathyroid hormone, Serum 25-OH Vitamin D, anti-nuclear antibody, anti-dsDNA antibodies, anti-ENA antibodies, rheumatoid factor, C3, C4, CH50, HLA typing, quantitative serum immunoglobulins, anti-streptolysin O titer		X								
HIV screen and hepatitis screen	X									
Total body photographs		X		X		X		X		X

Abbreviated Title: Anakinra in pustular dermatoses

Version Date: December 12, 2018

	Screening ≤8 weeks prior to enrollment	Baseline- up to drug initiation^a	Weeks 1, 2, 3 (+/- 3 days)	Week 4 (+/- 1 week)	Weeks 5, 6, 7 (+/- 3 days)	Week 8 (+/- 1 week)	Weeks 9, 10, 11 (+/- 3 days)	Week 12 (+/- 1 week): End of Treatm ent	Weeks 13, 14, 15 (+/- 3 days)	Week 16 (+/- 2 weeks): Post Therapy Follow- up^a
Total body surface area involvement measurement		X		X		X		X		X
PGA scoring		X		X		X		X		X
Skin biopsy	X ^g	X ^h						X ^h		
Quantiferon T gold	X ^d									
Chest X-ray if positive Quantiferon TB Gold	X ^d									
Microbiologic culture of pustule confirming noninfectious etiology	X									
FDG-PET CT scan		X						X		
Joint MRI		X						X		

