6.2.2 Disease Parameters

Measurable disease: Total body surface area involvement of pustules and erythematous plaques will be measured in this study. At the time of enrollment, all study participants will have active disease warranting systemic therapy, as defined by macroscopic non-infective pustular and inflammatory skin lesions involving $\geq 5\%$ of the total body surface area, or palmoplantar involvement.

Joint involvement will also be assessed using criteria set forth by the American College of Rheumatology.

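### The précis requires stable or worsening skin disease on background systemic therapy but criterion 2.1.1.4 does not, so the TBSAI50 rate may include improvement already under way

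*Combined protocol and SAP*

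**What the plan says.** The Eligibility list in the précis states: "Patients must have maintained a stable dose of immunosuppressant therapy, retinoids or anti-neutrophil therapy" and continues "for 2 weeks prior to study initiation with resultant stable or worsening skin disease". It therefore sets two conditions: a stable dose, and a disease course on that dose that is not improving.

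Criterion 2.1.1.4 in Section 2.1.1 states: "If taking immunosuppressants, retinoids or anti-neutrophil therapy, participants must maintain stable doses of these medications during the 2 weeks prior to study initiation". It keeps the stable dose, applies only to patients who take such drugs, and says nothing about disease course.

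Section 6.2.2 adds that at enrollment "all study participants will have active disease warranting systemic therapy, as defined by macroscopic non-infective pustular and inflammatory skin lesions involving" at least 5% of body surface, or palmoplantar involvement. This is a condition on extent at one time point.

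The primary endpoint (Sections 1.1.1, 6.2.1 and 8) is a reduction of at least 50% in TBSAI at week 12, in one open-label arm of 25 evaluable patients.

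**The concern.** In an uncontrolled before-after trial, the entry criteria are the main protection against counting improvement that would have happened anyway. The précis contains such a protection for patients on background systemic therapy: their disease must not be getting better on it. The criterion that investigators would be expected to apply leaves it out.

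Two weeks on an unchanged dose does not show that the effect of an earlier dose change has levelled off. A patient whose background drug was recently started or increased could enter while still improving, go on improving after baseline, and be counted as an anakinra responder. What is at stake is who may be enrolled and what the response rate means.

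**Working it through.** **1. The two texts side by side.**

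| Patient at entry | Précis | Criterion 2.1.1.4 |
|---|---|---|
| On background therapy, stable dose for 2 weeks, skin disease stable or worse | meets it | meets it |
| On background therapy, stable dose for 2 weeks, skin disease improving | fails it | meets it |
| Not on any such therapy | fails it if read literally | criterion does not apply |

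The second row is the point. The third is a side effect of the wording: the précis has no conditional opening, whereas 2.1.1.4 has one.

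**2. Does anything else supply the missing condition?**
- 2.1.1.2 and 6.2.2 require active disease, which 6.2.2 defines by extent and not by direction of change.
- 2.1.1.5 (stable topicals) and 2.1.2.5 (biologic washout) restrict other treatments, not disease course.
- 2.1.2.21 mentions interference with interpretation of results, but it concerns other medical or psychiatric conditions and laboratory abnormalities.
- Section 2.2 lists "Medical history and medication review" at screening, and Section 2.4 lists the baseline skin examination. Neither asks for a trend.
- In the Section 3.6 calendar, the row "Total body surface area involvement measurement" is marked at baseline and weeks 4, 8, 12 and 16, with no entry at screening.

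No section says that the précis or Section 2 prevails.

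**3. Which improvement would count?** TBSAI50 is measured from baseline. Take assumed values: TBSAI falls from 20% to 10% on background therapy before baseline. At 10% the patient still meets the 5% extent threshold. The earlier fall of 10 points does not count. To be a responder the patient must reach 0.5 × 10% = 5% or less by week 12. Only improvement that continues after baseline can contribute.

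**4. Direction and unit of size.** Let p be the response rate due to anakinra, f the share of patients still improving on background therapy at entry, and q the chance that such a patient reaches TBSAI50 without anakinra. If the two routes to response are independent,

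observed rate = p + (1 − p) × f × q.

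The excess is (1 − p) × f × q. The documents give neither f nor q, so the excess cannot be calculated. If the earlier improvement has levelled off, q is 0 and so is the excess. The formula also leaves out tapering of background drugs. As a unit only, one responder among 25 is 1/25 = 0.04, or 4 percentage points; how many of these would be due to background therapy, if any, is unknown.

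**5. Section 8 figures.**
- Half-width of the 95% interval at a 50% rate with 25 patients: 1.96 × √(0.5 × 0.5 / 25) = 1.96 × 0.1 = 0.196, which reproduces the stated 20%.
- One-sided 95% upper bound for 0 responders in 9: 1 − 0.05^(1/9) = 0.283, which reproduces the stated 28%.

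Both depend only on the numbers of patients and responders. Neither changes whichever eligibility text is adopted.

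**The case against.** The strongest reply is that 2.1.1.4 is silent on disease course and does not oppose the précis. For patients on background therapy, both texts can be applied together. The précis is also plainly a partial list: it omits the stable-topicals, tuberculosis and phototherapy criteria. It is right that this is an omission and not a direct contradiction, and the literal exclusion of untreated patients may be no more than compressed wording. But a summary normally shortens criteria, and this one adds a mandatory condition. The eligibility decision for an improving patient still depends on which text is used.

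A reader might infer that admitting such patients can only raise the TBSAI50 rate. The documents do not support that. Improvement before baseline does not count, improvement that has levelled off adds nothing, and Section 3.1 allows other immunosuppressants to be tapered once disease is quiescent, which could work against a background-driven response.

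A reader might also infer that the two sites will apply different rules. Section 2.3.1 refers to "A registration Eligibility Checklist from the web site", and Section 2.3.2 tells the participating site to "complete the protocol registration form which contains the eligibility checklist". The content of neither checklist is in the documents. Eligibility is confirmed centrally, the participating site must send source documents, and nothing shows that anyone registers patients from the précis. Divergence between sites is speculation.

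Two further points stand. Requiring stable or worsening disease may select some patients at the peak of a flare and so invite regression to the mean; Table 1 describes one of these diseases as episodic. And Section 8 plans an estimate with no success threshold, so no pass-or-fail decision on efficacy is put at risk.

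**Conclusion.** The concern holds in a limited form. Two current texts give different eligibility decisions for a patient still improving on a stable dose of background systemic therapy, and no other criterion settles it. If Section 2 is applied as written, background-driven improvement that continues after baseline would tend to raise the TBSAI50 rate and could not be told apart from an anakinra effect.

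Confidence is high on the difference in wording. On bias, the conclusion is only that it is possible and on balance upward. That rests on some patients entering while still improving and continuing to improve after baseline. The documents give no figure for either, so no size can be stated.

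**What to change.** Reconcile the précis, criterion 2.1.1.4 and the eligibility checklist so that all three state the same rule.

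- **Bias-reducing route for an uncontrolled endpoint:** add the précis's own condition of stable or worsening skin disease to 2.1.1.4 for patients on background systemic therapy. Keep the conditional opening of 2.1.1.4 in both texts, so that untreated patients are not excluded by wording. Have the investigator record the judgement at the baseline eligibility update already in the Section 3.6 calendar.
- **If the condition was dropped on purpose:** delete it from the précis and state in Section 8 that the response rate may include improvement due to background therapy.

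The first route costs one clause, a checklist line and one investigator statement, with no extra visit. Its downsides should be accepted openly. A few improving patients would be screened out in a rare disease. The judgement would rest on history and examination, because TBSAI is not scheduled at screening. The condition would not remove natural fluctuation or regression to the mean.

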2.1.3 Recruitment Strategies

Participants representing all ethnic groups and racial categories will be recruited for this study. Recruitment strategies may include a) referrals from NIH research physicians, b) referrals from non-NIH physicians, c) referrals from University of California, San Francisco (UCSF) and local area providers, d) NIH Patient Recruitment website, e) NIH Clinical Center Facebook page, f) print media including newspapers, specialized journals and magazines, g) advertisements posted on internet websites including Clinicaltrials.gov and ResearchMatch.org, local and regional dermatology association websites, h) interactions with patient and physician organizations in the local and national dermatology community including the National Psoriasis Foundation, i)

Abbreviated Title: Anakinra in pustular dermatoses

Version Date: December 12, 2018

dissemination of IRB approved flyers at designated locations, j) dissemination of IRB-approved recruitment letters sent to potentially eligible participants identified by investigators via review of our patient database and charts.

2.2 SCREENING EVALUATION

- Assessments to be completed prior to enrollment
 - Skin biopsy for hematoxylin and eosin staining to confirm diagnosis if prior confirmational biopsy has not been performed
 - Microbiologic culture of pustule confirming noninfectious etiology
- Assessments to be completed within 8 weeks prior to enrollment
 - Quantiferon TB gold
 - Chest X-ray to ensure absence of radiographic evidence of tuberculosis only if Quantiferon TB gold or tuberculin skin test is positive
 - Medical history and medication review
 - CBC with differential
 - Serum B-hCG in females of childbearing potential. Not required for females who are status-post hysterectomy or postmenopausal (no menses for >one year).
 - Blood urea nitrogen and serum creatinine
 - Anti-HIV-1/2 screen
 - Viral Markers Hepatitis Screen (HBsAg and anti-HCV)

2.3 REGISTRATION PROCEDURES

2.3.1 Registration at the Clinical Center

Authorized staff must register an eligible candidate with NCI Central Registration Office (CRO) within 24 hours of signing consent. A registration Eligibility Checklist from the web site (<http://home.ccr.cancer.gov/intra/eligibility/welcome.htm>) must be completed and sent via encrypted email to: NCI Central Registration Office [contact]. After confirmation of eligibility at Central Registration Office, CRO staff will call pharmacy to advise them of the acceptance of the patient on the protocol prior to the release of any investigational agents. Verification of Registration will be forwarded electronically via e-mail to the research team. A recorder is available during non-working hours.

2.3.2 For Participating Site Registration

A protocol registration form will be supplied by the NIAMS study coordinator and updates will be provided as needed. Subject eligibility and demographic information is required for registration. Once eligibility is confirmed, complete the protocol registration form which contains the eligibility checklist, indicating that the patient is being registered for treatment and send to NIAMS study coordinator. In addition, source documents supporting the eligibility criteria must be sent to the NIAMS study coordinator. The NIAMS study coordinator will notify you either by e-mail or fax that the protocol registration form has been received which will include the unique patient/subject ID number. Questions about eligibility should be directed to the study coordinator or PI. Questions related to registration should be directed to the study coordinator.

Abbreviated Title: Anakinra in pustular dermatoses

Version Date: December 12, 2018

2.3.3 Treatment Assignment and Randomization/ Stratification Procedures

Cohort

Number	Name	Description
1	Cohort 1	Subjects with pustular skin disease

Arm

Number	Name	Description
1	Arm 1	An initial dose of anakinra 100 mg/day will be administered daily via self-administered subcutaneous injection. If active disease persists at this dose, anakinra dose may be escalated to 200 mg/day injected subcutaneously daily at week 4 and 300mg/day at week 8

Stratifications

None

Randomization and Arm Assignment

This is an open-label non-randomized study. All subjects in cohort 1 will be directly assigned to arm 1.

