3 STUDY IMPLEMENTATION

3.1 STUDY DESIGN

This will be a phase 2, open label, prospective interventional 16-week dose titration study. Patients will complete a daily diary during the entire 16-week study course. Patients will be instructed to score the severity of rash, pustules, itch, skin pain, joint pain and overall well-being into their daily diaries. They will also document fever and doses of medications in their diaries.

(APPENDIX B: PATIENT)

At the baseline visit, clinical assessments, and laboratory, histopathologic and subjective data will be collected. All enrolled patients will initially receive treatment with anakinra 100 mg/day via self-administered subcutaneous injection. The first dose of anakinra will be administered under supervision in the clinic.

At week 4, disease response will be assessed by clinical exam, laboratory markers and evaluation of patient diaries that are returned to clinic. Determination for dose escalation will be made based on week 4 assessments. Those patients who do not achieve complete disease clearance with initial anakinra dosing will be increased to the next incremental dose level (see Section 3.1.2).

At week 8, patients will return for clinical evaluation and patients who do not achieve complete disease clearance on anakinra have the option of dose escalation up to the next incremental dose level. All patients will stop anakinra at week 12.

Patients will return for an Off Study visit at week 16, approximately 28 days after their final dose is administered. Considering personal/work/travel/other obligations, a period of no more than 1 week before or after the Week 4, 8, or 12 visits, and 2 weeks before or after the Week 16 visit may be permitted.

Total body photographs will be taken at baseline, week 4, week 8, week 12 and week 16 (at the investigator's discretion).

With the patient's consent, and at the discretion of the investigator, a skin biopsy for research will be taken at baseline and week 12. Skin biopsies will be taken from lesional and non-lesional skin. Non-lesional skin will be obtained for the purpose of comparison with lesional skin in immunohistochemistry, cytokine and gene expression studies, as well as in vitro keratinocytes studies.

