3.1.2 Dose Escalation

An initial dose of anakinra 100 mg/day will be administered daily via self-administered subcutaneous injection. If pustule formation persists at this dose, anakinra dose may be escalated up to 200 mg/day injected subcutaneously daily at week 4. Participants will be re-assessed at week 8, and if pustule formation persists and the patient weighs ≥ 75 kg, the dose may be escalated up to a maximum 300 mg/day.

Dose Escalation Schedule	
Dose Level	Dose of anakinra
Level -1*	50mg SC daily
Level 1	100 mg SC daily
Level 2	200 mg SC daily
Level 3	300 mg SC daily (patients ≥ 75 kg only)

Abbreviated Title: Anakinra in pustular dermatoses

Version Date: December 12, 2018

*Patients who experience an adverse event on dose level 1 that requires dose reduction may be reduced to dose level -1, 50mg SC daily (see Section 3.3). Patients who require dose reduction due to an adverse event at any point in this study will not be eligible for dose escalation.

Dose escalation will follow the rules outlined in the Table below.

Time of Assessment	Escalation Decision Rule
Baseline	
 Enter each patient onto study at dose level 1
Week 4	
 If patient has achieved complete clearance of pustular and plaque disease, remain at dose level 1 If patient has not achieved complete pustule and plaque clearance, increase to next incremental dose level
Week 8	
 If patient has achieved complete clearance of pustular and plaque disease, remain at current dose level If patient has not achieved complete clearance of pustular and plaque disease AND patient weighs ≥ 75kg, increase to next incremental dose level

If a patient experiences a Grade 2 adverse event probably or definitely related to anakinra within 7 days prior to a scheduled dose escalation, dose escalation will be postponed until resolution of the adverse event or a maximum of 14 days, whichever is shorter.

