3.2 DRUG ADMINISTRATION

Anakinra is supplied in single-use 1 ml prefilled glass syringes with 27 gauge needles as a sterile, clear, colorless-to-white, preservative-free solution for daily subcutaneous (SC) administration. Each 1 ml prefilled glass syringe contains: 0.67 ml (100 mg) of anakinra in a solution (pH 6.5) containing sodium citrate (1.29 mg), sodium chloride (5.48 mg), disodium EDTA (0.12 mg), and polysorbate 80 (0.70 mg) in water for injection, USP.

Patients will be instructed verbally and in writing that anakinra should be protected from light, stored in the refrigerator at 2°C to 8°C (36°F to 46°F) away from children, and never frozen. Patients will be instructed not to use any syringe if the solution appears discolored or cloudy or has been at room temperature ≥ 24 hours. Patients will be instructed to avoid shaking the pre-filled syringes, to use each syringe only once, and to inject the entire volume of solution. Patients will receive a diagram (**APPENDIX C: PATIENT HANDOUT**) of body sites where anakinra is to be injected, emphasizing the importance of avoiding veins, arteries and injecting into a new site each day. Self-injection demonstration and technique will be provided once the baseline visit has concluded.

All patients will be given a puncture-resistant container for proper disposal of syringes after use.

Abbreviated Title: Anakinra in pustular dermatoses

Version Date: December 12, 2018

All patients will initiate anakinra therapy with one 1ml (100 mg) prefilled syringe injected subcutaneously daily. Those who achieve disease quiescence on this dose by week 4 will continue at this dose until week 12.

Those who do not demonstrate disease quiescence at week 4 will increase their dose to 2-1ml prefilled syringes (total of 200 mg) to be injected subcutaneously daily. Those individuals who weight >75kg and do not demonstrate disease quiescence by week 8 on anakinra 200 mg/day will be instructed to increase their dose to 3-1ml prefilled syringes (total of 300mg) injected subcutaneously daily.

Patients who miss a dose will be instructed to administer the dose as soon as they remember. However, if it is almost time to administer the next dose, the patient will be directed to skip the missed dose and proceed with their regularly scheduled dose. Patients will be reminded to avoid double-dosing in an effort to make up the missed dose.

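### The Arm 1 definition (2.3.3) allows 300 mg/day at week 8 with no weight condition, while 3.1.2 limits that dose to patients of at least 75 kg and 3.2 and the précis to patients above 75 kg

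*Combined protocol and SAP*

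**What the plan says.** Five places in the protocol bear on the week-8 dose step.

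- **Section 2.3.3, Arm 1.** If active disease persists, the dose may be "escalated to 200 mg/day injected subcutaneously daily at week 4 and 300mg/day at week 8". No weight is mentioned. The same section assigns all subjects to this arm.
- **Section 3.1, week-8 paragraph.** It says "patients who do not achieve complete disease clearance on anakinra have the option of dose escalation up to the next incremental dose level". It names no dose and no weight. The week-4 paragraph just before it uses the same idea of a next level and does carry a reference: patients not clear "will be increased to the next incremental dose level (see Section 3.1.2").
- **Section 3.1.2.** The text says that if pustules persist at week 8 and "the patient weighs ≥ 75 kg, the dose may be escalated up to a maximum 300 mg/day". The dose-level table gives Level 3 as "300 mg SC daily (patients ≥ 75 kg only"). The week-8 row of the decision table also requires at least 75 kg.
- **Section 3.2.** The step to three syringes is for "Those individuals who weight >75kg and do not demonstrate disease quiescence by week 8 on anakinra 200 mg/day".
- **Précis, Design.** The dose can rise to 200 mg/day and "for patients $>75 \text{ kg}$ up to 300 mg/day at the end of week 8".

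In addition, footnote c of the study calendar (Section 3.6) sends the reader to 3.2 for the escalation criteria, whereas the reference in 3.1 goes to 3.1.2.

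**The concern.** The arm description is the regimen to which every subject is assigned, and it is the one place that names 300 mg/day without the weight restriction found elsewhere. A site working from it could take a lighter patient to a dose that the escalation schedule does not provide for. There are two sites, so they could also apply different rules.

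Three things are at stake. The first is exposure: who may receive the highest dose. The second is compliance: Section 7.2.1 requires all protocol deviations to be reported within 7 days, and here the same dosing decision is or is not a deviation depending on the section consulted. The third is description: adequate dosing and safety are secondary objectives (1.1.2), and Section 3.1 plans to use the recorded doses to assess the average amount of anakinra needed for the greatest improvement.

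**Working it through.** The plan states no figure on this point to reproduce, so the check sets the passages side by side.

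**Step 1. Weight condition for 300 mg/day at week 8**

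| Place | Condition |
|---|---|
| Précis | above 75 kg |
| 2.3.3, Arm 1 | none |
| 3.1, week-8 paragraph | none stated; no dose named |
| 3.1.2 (text, dose-level table, week-8 row) | at least 75 kg |
| 3.2 | above 75 kg |

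Three places carry a limit and two do not. The three limits use two different inequality signs.

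**Step 2. Patient on 200 mg/day with disease still active at week 8: is 300 mg/day allowed?**

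| Weight | 2.3.3 | 3.1.2 | 3.2 | Précis |
|---|---|---|---|---|
| below 75 kg | yes | no | no | no |
| exactly 75 kg | yes | yes | no | no |
| above 75 kg | yes | yes | yes | yes |

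The first row is the main conflict and covers every lighter patient. The second row covers only a recorded weight of exactly 75 kg.

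**Step 3. Section 3.1 against 3.1.2.** Section 3.1 offers the next level, and levels are defined only in 3.1.2. For a lighter patient on Level 2, the next level is Level 3, which is weight-limited where it is defined, so 3.1 read with its definitions does not offer that patient 300 mg/day. The two sections do differ in a narrower case. Take a patient below 75 kg who was clear at week 4, stayed on Level 1, and is no longer clear at week 8. Section 3.1 gives the option of the next level (200 mg/day). The week-8 row in 3.1.2 ties any increase to weighing at least 75 kg, so it provides none.

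**Step 4. Effect on the dose summary.** The protocol does not define the denominator of the average-dose summary. Assume it is the mean final dose over the 25 evaluable patients in Section 8. Each lighter patient who goes to 300 instead of staying at 200 mg/day then shifts the mean by

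(300 − 200) / 25 = 4 mg/day,

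and *k* such patients shift it by 4*k* mg/day. The documents give no weight distribution and no expected proportion still active at week 8, so *k* cannot be estimated.

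**Step 5. Effect on Section 8.** The primary estimate is one response proportion over all evaluable patients. The 25 patients, the stated interval half-width of 20 percentage points and the look at the first 9 patients do not depend on dose level. None of them changes.

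**The case against.** The best defence is that 2.3.3 is a short summary under registration procedures and is permissive, not mandatory. The operative text is in 3.1.2, which says that escalation follows its table, and that table has the weight condition. Both cross-references (3.1 to 3.1.2, and calendar footnote c to 3.2) lead to a weight-limited rule. Dose modifications must be discussed with the principal investigator (3.3), and the team reviews each patient weekly (7.4.1). An unintended 300 mg/day dose would need staff to rely on the summary and overlook three other places.

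Much of this stands, and it makes an actual dosing discrepancy less likely. It does not remove the contradiction: no text says that 3.1.2 prevails over 2.3.3, the précis is also a summary yet keeps the limit, and the two cross-references lead to different cut-offs.

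Three stronger readings are tempting, and the documents do not support them.

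- *That the limit is a 4 mg/kg cap, which 2.3.3 breaches.* The arithmetic 300/75 = 4.0 holds only within Level 3. No section gives a mg/kg ceiling or a reason for 75 kg. Level 2 has no weight condition, and 200/50 = 4.0, so any patient under 50 kg already exceeds 4 mg/kg under 3.1.2 itself. Section 11.1.2 also reports higher doses per kilogram in NOMID patients. No specific harm can be claimed.
- *That 3.1 openly offers 300 mg/day to everyone.* It names no dose and relies on the levels in 3.1.2 (Step 3).
- *That efficacy results at Level 3 would be contaminated.* Section 8 plans no analysis by dose level.

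**Conclusion.** The contradiction is in current text and rests on 2.3.3 alone: it permits 300 mg/day for any patient with active disease, against a weight restriction in 3.1.2, 3.2 and the précis. The different inequality signs and the week-8 wording of 3.1 are lesser inconsistencies of the same rule.

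The effect is on who may receive the highest dose, on what counts as a deviation, and on a descriptive dose summary (4 mg/day per discordant patient under the Step 4 assumption). The primary estimate's design and precision are untouched. How many patients would be affected is unknown from the documents. The conclusion needs no view on which limit is clinically appropriate, and none is taken here. It is worth correcting because the cost is small and the present text gives two answers to the same dosing question.

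**What to change.** Reconcile 2.3.3, 3.1, 3.1.2, 3.2, the précis and calendar footnote c to one week-8 rule with one inequality sign. The safer drafting is to keep the rule in a single schedule and have the other places refer to it instead of restating doses. That schedule should also say what happens at week 8 to a patient below the cut-off who is still on Level 1. The sponsor decides which rule applies.

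The cost is a wording amendment. No change to sample size, endpoints, visits or the analysis in Section 8 is needed. If patients have already been escalated, their weight and dose at week 8 should be checked against the rule that is adopted, so that deviations are classified in one way at both sites.
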